## REVISION HISTORY

Ver. No.	Description of Change(s)	Effective Date
2.0	
Section 1.3, Schedule of Activities and Section 4.1, Overall Design: The amount of blood obtained for analysis of platelet FcγRIIa changed from 'approximately 30 ml or 2 tablespoons' to 'approximately 3 ml to 6 ml.'
 
Section 1.1 Synopsis, Section 4.1 Overall Design and Section 4.2 End of Study Definition: The duration of subject follow-up was clarified. Text was changed from 'the last subject enrolled has completed 18 months of follow-up' to 'the last subject enrolled has completed at least 18 months of follow-up.'
 
Section 9.1 Statistical Hypotheses: Updated study hypotheses to match those in Section 2.2 Study Hypothesis. Text updated to read as follows:
 

1. Platelet expression of FcγRIIa is associated with risk of MI, stroke, and death

2. Incorporating platelet expression of FcγRIIa into existing risk scores improves identification of patients at high risk of MI, stroke, and death

3. Platelet expression of FcγRIIa is not associated with risk of major bleeding

 
Miscellaneous minor changes to punctuation, grammar and abbreviations made throughout document.
	1 December 2021
3.0	
Section 1.1 Synopsis: The age of subjects eligible and type of MI (type 1) were clarified. Text updated to read as follows: Approximately 800 male and female subjects ≥ 18 years of age with confirmed type 1 MI [ST-segment elevation MI (STEMI) or non-ST-segment elevation MI (NSTEMI)] will be enrolled before hospital discharge for the index event
 
Section 5.1 Inclusion Criteria: The age of subjects eligible and type of MI (type 1) were clarified. Text updated to read as follows:
 

1. Male or female subjects ≥ 18 years of age hospitalized with confirmed type 1 MI (STEMI or NSTEMI), referred to as the index event (described in Appendix 1)

 
Section 1.2 Study Schematic, Section 4.1 Overall Design, and Figure 5 Schematic Overview of the Study: Specified that the type of MI for study eligibility is type 1 MI.
	3 February 2022

Ver. No.	Description of Change(s)	Effective Date
4.0	
Section 1.1 Synopsis, Section 2.3 Evidence for Use of FcγRIIa as a Tool, and Section 4.1 Overall Design: Updated to allow for limited enrollment of select subjects receiving anticoagulants. Text has been added as follows: Enrollment of subjects who are receiving anticoagulants for atrial fibrillation or venous thromboembolic disease will be limited to approximately 100 subjects.
 
Section 1.1 Synopsis and Section 4.1 Overall Design: Increased the number of participating sites from 'approximately 10' to 'approximately 10-20'.
 
Section 1.3 Schedule of Activities, Section 4.1 Overall Design and Section 8.1 Efficacy and Safety Assessments: Expanded the time window for blood draw for quantification of FcγRIIa. The following text has been added: Blood can be taken up to 2 weeks post-study enrollment.
 
Section 5.2 Exclusion Criteria: Deleted Exclusion Criterion 1 'Requirement for treatment with full dose-anticoagulant therapy (e.g., for atrial fibrillation).
	20 October 2022
4.1 (Site Specific)	
1.1 Synopsis: Added information on the substudy including objective, endpoint and study population. The following text has been added: Substudy: A substudy will be performed at some sites. Substudy Objective: Demonstrate that the FcγRIIa assay provides a consistent measure of platelet expression of FcγRIIa by measuring a second blood sample after study enrollment. Substudy Endpoint: Measurement of platelet expression of FcγRIIa 2 to 6 weeks after study enrollment which will be compared to FcγRIIa results from the first/baseline blood sample. Study Population: Subjects enrolled in the parent study are eligible
 
1.3 Schedule of Activities: Added blood sample to quantify FcγRIIa 2 to 6 weeks after enrollment into the study.
	See Header
	
Section 4.3 Substudy. New section added to describe the background, objective, endpoint and subject eligibility of the substudy. The following text has been added: Platelet function tests exhibit substantial intra-individual variability when measures are repeated 2 to 6 weeks after initial testing (Frelinger 2013, Hochholzer 2014, Nührenberg 2015). Results from a study in healthy subjects suggest that FcγRIIa will vary by <10% over the course of 2 to 6 weeks (McMahon 2019). The objective of the substudy is to demonstrate that the FcγRIIa assay provides a consistent measure of platelet expression of FcγRIIa by measuring a second blood sample after study enrollment and the first/baseline blood sample is
	

taken. The substudy endpoint is the measurement of platelet expression of FcγRIIa 2 to 6 weeks after study enrollment. The substudy will be performed at some sites identified by early study start-up and prior experience in similar studies. Subjects enrolled in the parent study are eligible for the substudy. A second sample of blood will be obtained by phlebotomy 2 to 6 weeks after the subject is enrolled in the study. The results from this second sample of blood will be compared to FcγRIIa results from the first/baseline blood sample. See Section 2.4 for the risk/benefit assessment associated with phlebotomy and the second blood draw.
	

Section 9.4.7 Substudy Analyses. New section added regarding substudy analyses. The following text has been added: Details on the substudy statistical analyses will be summarized in the SAP.
	

## ABBREVIATIONS

ACS	Acute Coronary Syndrome
AE	Adverse Event
ASA	Acetylsalicylic Acid; Aspirin
BARC	Bleeding Academic Research Consortium
ARCTIC	Assessment by a Double Randomization of a Conventional Antiplatelet Strategy versus a Monitoring-guided Strategy for Drug-Eluting Stent Implantation and of Treatment Interruption versus Continuation One Year after Stenting
CFR	Code of Federal Regulations
CKD	Chronic Kidney Disease
CI	Confidence Interval
CRF	Case Report Form
CV	Coefficient of Variation
DAPT	Dual Antiplatelet Therapy
DM	Diabetes Mellitus
Fc	Fragment Constant
eCRF	Electronic Case Report Form
FcγRIIa	FcGammaRIIa
FDA	Food and Drug Administration
GCP	Good Clinical Practice
GFR	Glomerular Filtration Rate
GRAVITAS	Gauging Responsiveness with A VerifyNow assay-Impact on Thrombosis And Safety
HIPAA	Health Insurance Portability and Accountability Act
HR	Hazard Ratio
ICH	International Conference on Harmonisation
Ig	Immunoglobulin
IRB	Institutional Review Board
MI	Myocardial infarction
ml	milliliter
MVD	Multi-Vessel Coronary Artery Disease
ng	nanogram
nM	nanomolar
NSTEMI	Non-ST-segment elevation myocardial infarction
PCI	Percutaneous Coronary Intervention
QC	Quality Control
REDCap	Research Electronic Data Capture
REDUCE	Evaluation of short-term dual antiplatelet therapy in patients with acute coronary syndrome treated with a new-generation stent
SAE	Serious Adverse Event
SAP	Statistical Analysis Plan
SMART-DATE	6-month versus 12-month or longer dual antiplatelet therapy after percutaneous coronary intervention in patients with acute coronary syndrome
STEMI	ST-segment elevation myocardial infarction
SUSAR	Suspected Unexpected Serious Adverse Reaction
TIMI	Thrombolysis in Myocardial Infarction
TWILIGHT	Ticagrelor with or without Aspirin in High-Risk Patients after PCI
μg	microgram
U	Units
US	United States

## STATEMENT OF COMPLIANCE

This study will be carried out in accordance with International Conference on Harmonisation Good Clinical Practice (ICH GCP) and the following:

- United States (US) Code of Federal Regulations (CFR) applicable to clinical studies (45 CFR Part 46, 21 CFR Part 50, 21 CFR Part 56, and/or 21 CFR Part 312.)

The protocol, informed consent form(s), recruitment materials, and all participant materials will be submitted to the Institutional Review Board (IRB) for review and approval. Approval of both the protocol and the consent form must be obtained before any subject is enrolled. Any amendment to the protocol will require review and approval by the IRB before the changes are implemented to the study. In addition, all changes to the consent form will be IRB-approved; a determination will be made regarding whether a new consent needs to be obtained from subjects who provided consent, using a previously approved consent form.

## 1 PROTOCOL SUMMARY

### 1.1 SYNOPSIS

Title:	Assessment of Individual Risk of Cardiovascular Events by Platelet FcGammaRIIa (FcγRIIa)
Study Description:	A Prospective, Observational Multicenter Non-Interventional Cohort Study
Objectives:	
The primary objective is to determine whether platelet expression of FcγRIIa is associated with risk of myocardial infarction (MI), stroke and death.
 
Secondary objectives include:
 

• Develop a score that combines clinical characteristics plus platelet expression of FcγRIIa to determine the risk of MI, stroke, and death.

• Determine whether platelet expression of FcγRIIa is associated with risk of major bleeding.

Endpoints:	
The primary endpoint is the composite of death, MI, and stroke.
 
A secondary endpoint is the incidence of clinically significant bleeding according to the Bleeding Academic Research Consortium (BARC) scale type 2-5.

Study Population:	
Approximately 800 male and female subjects ≥ 18 years of age with confirmed type 1 MI [ST-segment elevation MI (STEMI) or non-ST-segment elevation MI (NSTEMI)] will be enrolled before hospital discharge for the index event. Subjects with increased risk of an event, defined as ≥2 of the following risk factors, will be eligible:
 

• Age ≥65

• Multi-vessel coronary artery disease (MVD) defined as ≥2 vessels or left main with a stenosis ≥50%

• Chronic Kidney Disease (CKD) defined as estimated glomerular filtration rate (GFR) <60 ml/min/1.73 m^2

• Diabetes mellitus (DM)

• Prior MI

 
Enrollment of subjects who are receiving anticoagulants for atrial fibrillation or venous thromboembolic disease will be limited to approximately 100 subjects.

Phase:	Not Applicable
Number of Sites	Approximately 10-20 sites in the United States will participate in this study.
Study Intervention:	Not Applicable
Study Duration:	It is anticipated that it will take approximately 12 months to enroll approximately 800 subjects. The study and subject follow-up will continue until 1) at least 80 ischemic events (MI, stroke, and death) have occurred, and 2) the last subject enrolled has completed at least 18 months of follow-up.
Participant Duration:	After enrollment, all subjects will be followed until the end of the study that will be at least 18 months after enrollment of the last subject. Based on an annual ischemic event rate of 10%, the overall length of participation in the study is anticipated to be up to 3 years.

**Substudy:** A substudy will be performed at some sites.

[figure not shown]
**Substudy Objective:** Demonstrate that the FcγRIIa assay provides a consistent measure of platelet expression of FcγRIIa by measuring a second blood sample after study enrollment.

**Substudy Endpoint:** Measurement of platelet expression of FcγRIIa 2 to 6 weeks after study enrollment which will be compared to FcγRIIa results from the first/baseline blood sample

**Study Population:** Subjects enrolled in the parent study are eligible.

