The primary endpoint will be the composite of death, MI, and stroke. MI will be defined in accordance with the 4th universal definition (Thygesen 2018) and stroke consistent with consensus guidelines (Sacco 2013). The incidence of clinically significant bleeding will be determined using the Bleeding Academic Research Consortium (BARC) scale (Mehran 2011) and is defined as BARC type 2-5. Study endpoint events will be confirmed by the review of medical records by the investigator and all relevant medical records will be obtained by the site for submission to the sponsor (as described in Section 10.8). Subjects who experience an endpoint event will continue to be followed throughout the entire study and any subsequent endpoint events will also be confirmed and recorded. See Appendix 1 for study endpoint event definitions.

A total of approximately 800 subjects will be enrolled at approximately 10-20 sites in the US. It is anticipated that it will take about 12 months to enroll the total number of subjects. The study and subject follow-up will continue until 1) at least 80 ischemic events (MI, stroke, and death) have occurred, and 2) the last subject enrolled has completed at least 18 months of follow-up. Based on an annual ischemic event rate of 10%, the overall length of participation in the study is anticipated to be up to 3 years. Results will be monitored during the course of the study.

Figure 5 Schematic Overview of the Study

MI=myocardial infarction; NSTEMI= non-ST-segment elevation MI, STEMI= ST-segment elevation MI

\* Subjects who experience an endpoint event will continue to be followed throughout the entire study and any subsequent events will also be confirmed and recorded.

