#### 9.2 SAMPLE SIZE DETERMINATION

This study is designed to provide a sufficient number of events to build and evaluate a prediction model. The planned sample size of 800 subjects will continue until at least 80 ischemic events have occurred. Under the guideline from Steyerberg of 10 events required per predictor (Steyerberg 2019), this sample size will allow a model with FcγRIIa and up to seven additional predictors to be built. Preliminary results ([name] 2018) suggest that a 4-fold greater incidence of events will be seen in subjects with high platelet expression of FcγRIIa. For

the primary endpoint, there will be at least 95% power to detect a 2-fold greater incidence of cardiovascular endpoints (MI, stroke, and death) with a two-sided  $\alpha < 0.01$  assuming 8% of subjects experience the endpoint. With the planned sample size of 800 a hazard ratio (HR) of 1.9 with a  $p=0.04$  (lower bound of the 95% CI of 1.2) can be detected. For the secondary endpoint, there will be 95% power to detect a hazard ratio of 1.93 when comparing bleeding risk in subjects with high compared with low FcγRIIa expression when assuming a two-sided  $\alpha=0.05$  and 5% of subjects experience bleeding in the low FcγRIIa expression group.

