5.10 Determination of Sample Size

This study is designed to provide a sufficient number of events to build and evaluate a prediction model. The planned sample size of 800 subjects will continue until at least 80 ischemic events have occurred. Under the guideline from Steyerberg of 10 events required per predictor (Steyerberg 2019), this sample size will allow a model with FcγRIIa and up to seven additional predictors to be built. Preliminary results ([name] 2018) suggest that a 4-fold greater incidence of events will be seen in subjects with high platelet expression of FcγRIIa. For the primary endpoint, there will be at least 95% power to detect a 2-fold greater incidence of cardiovascular endpoints (MI, stroke, and death) with a two-sided $\alpha < 0.01$ assuming 8% of subjects experience the endpoint. With the planned sample size of 800 a hazard ratio (HR) of 1.9 with a $p=0.04$ (lower bound of the 95% CI of 1.2) can be detected. For the secondary endpoint, there will be 95% power to detect a hazard ratio of 1.93 when comparing bleeding risk in subjects with high compared with low FcγRIIa expression when assuming a two-sided $\alpha = 0.05$ and 5% of subjects experience bleeding in the low FcγRIIa expression group.

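### The 8% event proportion behind the sample size has no time window or group, conflicts with the plan's own 10% per year (and, if overall, its 80-event target), and does not give the stated 95% power

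*Protocol*

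**What the plan says.** Two event assumptions appear in current text.

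- **Duration.** Protocol 1.1 plans on an "annual ischemic event rate of 10%, the overall length of participation in the study is anticipated to be up to 3 years", and Protocol 4.1 repeats the sentence. The rate agrees with the registry figure in Protocol 2.3 of 9.7 per 100 patient-years for patients with at least two of the enrolment risk factors.
- **Sizing.** Protocol 9.2 claims at least 95% power for a 2-fold difference in the primary endpoint, "assuming 8% of subjects experience the endpoint". SAP 5.10 repeats the claim "with a two-sided $\alpha < 0.01$ assuming 8% of subjects experience the endpoint". Neither says over what period the 8% accrues, or whether it is the overall proportion or that of the low-expression group.
- **Event target.** The same paragraph says: "The planned sample size of 800 subjects will continue until at least 80 ischemic events have occurred".
- **Timeline.** Protocol 1.1 anticipates that "it will take approximately 12 months to enroll approximately 800 subjects". Under Protocol 4.2 the study ends only when 80 events are confirmed and the last subject has at least 18 months of follow-up.

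**The concern.** An annual rate and a cumulative proportion can agree only if the period linking them is given, and it is not. At the earliest planned end, mean follow-up is about 24 months. A group with a 10% annual rate would by then have far more than 8% of subjects with an event. If the 8% is the overall proportion, it also falls short of the event count that its own paragraph requires.

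The power claim is what is at stake, because the 8% is its stated input. A reader cannot tell whether the 95% refers to about 64, 80 or 150 events, and these give very different power. The expected number of events at the final analysis, and which of the two closing conditions is likely to apply, are uncertain for the same reason.

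**Working it through.** **Inputs.** 800 subjects, at least 80 events, 12-month accrual and 18 months after the last enrolment (Protocol 1.1, 9.2). Event rate 10% per year (1.1, 4.1) or 9.7 per 100 patient-years (2.3). 8%, 2-fold effect and two-sided alpha 0.01 (9.2, SAP 5.10). High-expression share 55% in the pilot (2.3); 50% is also tried. Assumed, because not stated: uniform accrual, constant rate, no loss.

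**1. The plan's own figure: 95% power with 8%.** Comparison of two proportions with pooled null variance: power = Φ{[(p2 − p1) − 2.576·SE0] / SE1}.

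- 8% overall, 400 per group: p1 = 5.33%, p2 = 10.67%, SE0 = 0.01918, SE1 = 0.01909. (0.05333 − 0.04941)/0.01909 = 0.205, so power is 58%. With 440 high and 360 low it is 54%.
- 8% in the low group, so 8% against 16%: (0.0800 − 0.0592)/0.0228 = 0.91, so power is 82%. With 440 high and 360 low it is 81%.

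Neither reading reproduces 95%.

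**2. The same question by event count** (Schoenfeld): power = Φ[ln 2 · √(D·π(1−π)) − 2.576].

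| Events D | Power, π = 0.50 | Power, π = 0.55 |
|---|---|---|
| 64 (8% of 800) | 58% | 57% |
| 80 (the floor) | 70% | 69% |
| 145 | 94% | 94% |
| 152 | 96% | 95% |

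For 95% at π = 0.50: (2.576 + 1.645)² / (0.25 × 0.4805) = 148.3, so 149 events.

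**3. Events expected at about 10% per year.** With t in years from first enrolment, E(t) = 800·{1 − [exp(−r(t−1)) − exp(−rt)]/r}. For r = 0.10 and t = 2.5: [0.8607 − 0.7788]/0.10 = 0.819, so E = 800 × 0.181 = 145.

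| Reading of the rate | Events at month 30 | Share of 800 | Ratio to 8% | 80th event |
|---|---|---|---|---|
| 9.7 per 100 patient-years | 141 | 17.6% | 2.20 | month 19.1 |
| hazard 0.10 | 145 | 18.1% | 2.26 | month 18.7 |
| annual risk 10% | 152 | 19.0% | 2.37 | month 18.1 |

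With loss of 5% to 10% per year (assumed), these become 128 to 145 events, with the 80th at month 18.4 to 19.9.

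**4. Event target.** 0.08 × 800 = 64, below 80.

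**5. Duration.** At 10% per year, 80 events are reached well before month 12 + 18 = 30. The 18-month condition therefore sets the end, and the longest participation is about 2.5 years.

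**6. Effect of the missing window.** If the 8% is overall and accrues over the window shown, at a constant rate:

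| Window for the 8% | 80th event | 10% per year over the same window, relative to 8% |
|---|---|---|
| 12 months | month 21 | 1.2 |
| 20 months (pilot average follow-up) | month 31 | 1.9 to 2.0 |
| 24 months | month 36 | 2.3 to 2.4 |
| 30 months | month 44 | 2.8 to 2.9 |

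**The case against.** A reader might infer that the 3-year figure was really worked out from the 8%, because an 8% risk over 24 months puts the 80th event at month 36. The documents do not support this. No passage links the 8% to duration, and the match needs a window that is not stated. The 8% equals the pilot's overall proportion, and over the pilot's 20-month average follow-up the 80th event falls at about month 31.

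Nor does the 3-year figure contradict 10% per year. It is an upper bound that contains 30 months. Accrual is only anticipated, and 18 months of it would give exactly 36. What remains is that the bound is not derived from the rate cited for it.

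A single 2.4-fold discrepancy also says too much, because the ratio depends on window and group. The bleeding sentence of the same paragraph puts its 5% in the low-expression group. If the 8% is read that way, 360 × 0.08 + 440 × 0.16 = 99 events are expected, which clears the target of 80. Power is still only 81% to 82%.

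The most generous reading takes the 8% as annual. Over 24 months that gives about 89% to 90% power if overall, and 97% to 98% if it is the low group's rate. The sentence speaks of subjects, not a yearly rate. The low-group version also implies 360 × (1 − 0.92²) + 440 × (1 − 0.92⁴) = 180 events, or 22.5%, which again disagrees with 10% per year.

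Finally, a reader might think the allowance of FcγRIIa plus seven predictors depends on which rate is right. It does not: it is built on the 80-event floor, and the joint closing rule is well defined under either rate.

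**Conclusion.** The point stands as an unreconciled planning input. The 8% lacks a window and a group and disagrees with the plan's 10% per year: 17.6% to 19.0% against 8%, a ratio of 2.2 to 2.4 if the 8% is overall at 24 months' mean follow-up. If overall, it also misses the event target, 64 against 80.

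As a proportion of subjects it does not support the stated 95% power: about 54% to 58% overall, or 81% to 82% in the low group. About 149 events are needed. The 145 to 152 implied by 10% per year come close at 94% to 96%, so the 8% may simply be mislabelled, but the documents do not confirm that.

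These figures assume uniform accrual, a constant rate, no loss, and an unadjusted high-against-low comparison with 50% to 55% of subjects in the high group. The conduct of the study is not in question; the stated basis for its power and duration is.

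**What to change.** Use one annual event rate in Protocol 1.1, 4.1, 9.2 and SAP 5.10, and derive the other figures from it.

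- **If the registry-based 10% per year stands:** replace the 8% with about 18% overall (about 145 first events at month 30). Restate power on that count (about 94%) and at the 80-event floor (about 70%). Say that the 18-month condition is expected to end the study at about month 30, and keep the 3-year bound only as an allowance for slower accrual.
- **If the 8% is kept:** state its time window and group, restate the power it gives, and reconcile it with the 80-event target and the 10% per year.

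The change is to wording in four sections; enrolment and follow-up are unaffected. The cost is that the plan must show a less favourable power figure at the event floor.

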## 1.2 STUDY SCHEMATIC

Figure 1 Schematic Overview of the Study

MI=myocardial infarction; NSTEMI= non-ST-segment elevation MI, STEMI= ST-segment elevation MI

\* Subjects who experience an endpoint event will continue to be followed throughout the entire study and any subsequent events will also be confirmed and recorded.

## 1.3 SCHEDULE OF ACTIVITIES

Procedures	Day 1 (prior to or on day of hospital discharge) a	Week 2 to Week 6 after study enrollment	Telephone Study Visit every 6 months (+/- 4 weeks)	Final Telephone Study Visit (+ 2 weeks after at least 80 ischemic events accrued)
Informed Consent	X			
Inclusion/Exclusion Criteria	X			
Clinical Characteristics	X			
Enrollment	X			
Anti-thrombotic Medication Review	X		X	X
Blood Sample to Quantify FcγRIIa b	X	X d		
Assess for Study Endpoints c			X	X
Complete Case Report Forms (CRFs)	X		X	X
	
a: Procedures can be done at any time after confirmation of myocardial infarction index event and prior to hospital discharge. Day 1 is defined as the day the subject is enrolled into the study and must occur prior to or on the day of hospital discharge.
 
b: Approximately 3 ml to 6 ml blood sample. Blood can be taken up to 2 weeks post-study enrollment.
 
c: Endpoints include Ischemic events (MI, stroke, death) and clinically significant bleeding BARC type 2-5.
 
d: For sites participating in the substudy, a 3 ml to 6 ml blood sample will be drawn 2 to 6 weeks after enrollment into the study
			

